8 ETHICS

8.1 Institutional Review Board

Federal regulations and the ICH guidelines require that approval be obtained from an IRB before participation of human subjects in research studies. Before study onset, the protocol, informed consent, advertisements to be used for the recruitment of study subjects, and any other written information regarding this study to be provided to the subject or the subject's legal guardian must be approved by the IRB. Documentation of all IRB approvals and of the IRB compliance with ICH harmonized tripartite guideline E6 (R1): GCP will be maintained by the site and will be available for review by the Sponsor or its designee.

All IRB approvals should be signed by the IRB chairman or designee and must identify the IRB name and address, the clinical protocol by title or protocol number or both, and the date approval or a favorable opinion was granted.

The Investigator is responsible for providing written summaries of the progress and status of the study at intervals not exceeding 1 year or otherwise specified by the IRB. The Investigator must promptly supply the Sponsor or its designee, the IRB, and, where applicable, the institution, with written reports on any changes significantly affecting the conduct of the study or increasing the risk to subjects.

8.2 Ethical Conduct of the Study

The study will be performed in accordance with the ethical principles that have their origin in the Declaration of Helsinki, ICH GCP, and all applicable regulations.

8.3 Subject Information and Consent

A written informed consent in compliance with US Title 21 Code of Federal Regulations (CFR) Part 50 shall be obtained from each subject before entering the study or performing any unusual or non-routine procedure that involves risk to the subject. An informed consent template may be provided by the Sponsor to investigative sites. If any institution-specific modifications to study-related procedures are proposed or made by the site, the consent should be reviewed by the Sponsor or its designee or both before IRB submission. Once reviewed, the consent will be submitted by the Investigator to his or her IRB for review and approval before the start of the study. If the ICF is revised during the course of the study, all active participating subjects must sign the revised form.

Before recruitment and enrollment, each prospective subject or his or her legal guardian will be given a full explanation of the study and be allowed to read the approved ICF. Once the Investigator is assured that the subject/legal guardian understands the implications of participating in the study, the subject/legal guardian will be asked to give consent to participate in the study by signing the ICF.

The Investigator shall retain the signed original ICF(s) and give a copy of the signed original form to the subject or legal guardian.

9 INVESTIGATOR'S OBLIGATIONS

The following administrative items are meant to guide the Investigator in the conduct of the study but may be subject to change based on industry and government standard operating procedures, working practice documents, or guidelines. Changes will be reported to the IRB but will not result in protocol amendments.

9.1 Confidentiality

All laboratory specimens, evaluation forms, reports, and other records will be identified in a manner designed to maintain subject confidentiality. All records will be kept in a secure storage area with limited access. Clinical information will not be released without the written permission of the subject (or the subject's legal guardian), except as necessary for monitoring and auditing by the Sponsor, its designee, the FDA, or the IRB.

The Investigator and all employees and coworkers involved with this study may not disclose or use for any purpose other than performance of the study any data, record, or other unpublished, confidential information disclosed to those individuals for the purpose of the study. Prior written agreement from the Sponsor or its designee must be obtained for the disclosure of any said confidential information to other parties.

9.2 Financial Disclosure and Obligations

Investigators are required to provide financial disclosure information to allow the Sponsor to submit the complete and accurate certification or disclosure statements required under 21 CFR 54. In addition, the Investigator must provide to the Sponsor a commitment to promptly update this information if any relevant changes occur during the course of the investigation and for 1 year following the completion of the study.

Neither the Sponsor nor IQVIA is financially responsible for further testing or treatment of any medical condition that may be detected during the screening process. In addition, in the absence of specific arrangements, neither the Sponsor nor IQVIA is financially responsible for further treatment of the subject's disease.

9.3 Investigator Documentation

Before beginning the study, the Investigator will be asked to comply with ICH E6 (R1) Section 8.2 and Title 21 of the CFR by providing the following essential documents, including but not limited to:

- IRB approval
- Original signed Investigator agreement page of the protocol
- Form FDA 1572, fully executed, and all updates on a new fully executed Form FDA 1572
- Curriculum vitae for the Investigator and each Sub-Investigator listed on Form FDA 1572

- Financial disclosure information to allow the Sponsor to submit complete and accurate certification or disclosure statements required under 21 CFR 54. In addition, the Investigators must provide to the Sponsor a commitment to promptly update this information if any relevant changes occur during the course of the investigation and for 1 year after the completion of the study.
- IRB-approved informed consent, samples of site advertisements for recruitment for this study, and any other written information regarding this study that is to be provided to the subject or legal guardian, and
- Laboratory certifications and normal ranges for any local laboratories used by the site, in accordance with 42 CFR 493

9.4 Study Conduct

The Investigator agrees that the study will be conducted according to the principles of ICH E6 (R1). The Investigator will conduct all aspects of this study in accordance with all national, state, and local laws or regulations. Study information from this protocol will be posted on publicly available clinical trial registers before enrollment of subjects begins.

9.5 Adherence to Protocol

The Investigator agrees to conduct the study as outlined in this protocol in accordance with ICH E6 (R1) and all applicable guidelines and regulations.

9.6 Adverse Events and Study Report Requirements

By participating in this study the Investigator agrees to submit reports of SAEs according to the time line and method outlined in the protocol. In addition, the Investigator agrees to submit annual reports to the study site IRB as appropriate.

9.7 Investigator's Final Report

Upon completion of the study, the Investigator, where applicable, should inform the institution; the Investigator/institution should provide the IRB with a summary of the study's outcome and the Sponsor and regulatory authority with any reports required.

9.8 Records Retention

Essential documents should be retained until at least 2 years after the last approval of a marketing application in an ICH region and until there are no pending or contemplated marketing applications in an ICH region, or at least 2 years have elapsed since the formal discontinuation of clinical development of the study drug. These documents should be retained for a longer period, however, if required by the applicable regulatory requirements or by an agreement with the Sponsor. It is the responsibility of the Sponsor to inform the Investigator/institution as to when these documents no longer need to be retained.

9.9 Publications

After completion of the study, the data may be considered for reporting at a scientific meeting or for publication in a scientific journal. In these cases, the Sponsor will be responsible for these activities and will work with the Investigators to determine how the manuscript is written and edited, the number and order of authors, the publication to which it will be submitted, and other related issues. The Sponsor has final approval authority over all such issues.

Data are the property of the Sponsor and cannot be published without prior authorization from the Sponsor, but data and publication thereof will not be unduly withheld.

10 STUDY MANAGEMENT

10.1 Monitoring

10.1.1 Monitoring of the Study

The clinical monitor and/or designee, as a representative of the Sponsor, has the obligation to follow the study closely. In doing so, the monitor will visit the Investigator and study site at periodic intervals, in addition to maintaining necessary telephone and letter contact. The monitor will maintain current personal knowledge of the study through observation, review of study records and source documentation, and discussion of the conduct of the study with the Investigator and personnel.

All aspects of the study will be carefully monitored, by the Sponsor or its designee, for compliance with applicable government regulation with respect to current GCP and current standard operating procedures.

10.1.2 Inspection of Records

Investigators and institutions involved in the study will permit study-related monitoring, audits, IRB review, and regulatory inspections by providing direct access to all study records. In the event of an audit, the Investigator agrees to allow the Sponsor, representatives of the Sponsor, or a regulatory agency (e.g. FDA or other regulatory agency) access to all study records.

The Investigator should promptly notify the Sponsor and IQVIA of any audits scheduled by any regulatory authorities and promptly forward copies of any audit reports received to the Sponsor.

10.2 Management of Protocol Amendments and Deviations

10.2.1 Modification of the Protocol

Any changes in this research activity, except those necessary to remove an apparent, immediate hazard to the subject, must be reviewed and approved by the Sponsor or its designee. Amendments to the protocol must be submitted in writing to the Investigator's IRB for approval before subjects can be enrolled into an amended protocol, and before the changes can be implemented.

10.2.2 Protocol Deviations

The Investigator or designee must document and explain in the subject's source documentation any deviation from the approved protocol. The Investigator may implement a deviation from, or a change of, the protocol to eliminate an immediate hazard to study subjects without prior IRB approval. As soon as possible after such an occurrence, the implemented deviation or change, the reasons for it, and any proposed protocol amendments

should be submitted to the IRB for review and approval, to the Sponsor for agreement, and to the regulatory authorities, if required.

A protocol deviation is defined as an unintended or unanticipated departure from the procedures or processes approved by the Sponsor and the IRB and agreed to by the Investigator. A major deviation occurs when there is not adherence to the protocol by the subject or Investigator that results in a significant, additional risk to the subject. Major deviations can include not adhering to inclusion or exclusion criteria, enrollment of the subject without prior Sponsor approval, or not adhering to FDA regulations or ICH GCP guidelines, and will lead to the subject being withdrawn from the study ([Section 1](#)).

Protocol deviations will be documented by the clinical monitor throughout the course of monitoring visits. Investigators will be notified in writing by the monitor of deviations. The IRB should be notified of all protocol deviations in a timely manner.

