4.2 Withdrawal of Subjects from the Study

The duration of the study is defined for each subject as the date signed written informed consent is provided through the End of Study assessment, which will be on Day 35 or the date of Early Termination (ET) for subjects who are withdrawn prior to the End of Study assessment.

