4.2.1 Reasons for Withdrawal/Discontinuation

Subjects may withdraw from the study at any time and for any reason without prejudice to their future medical care by the Investigator or at the study site. Every effort should be made to keep subjects in the study and, in the case of voluntary withdrawal, to inquire as to the reason(s) for withdrawal. The reasons for subjects not completing the study will be recorded.

If a subject withdraws for any reason after having received study drug, the subject will be asked to complete ET procedures, which will be the same as those scheduled to be performed prior to discharge from the CRU on Day 8. If a subject voluntarily withdraws before receiving the study drug, no additional safety assessments or testing will be required.

A subject may be withdrawn from the study for any of the following reasons:

1. Does not meet the protocol inclusion or exclusion criteria.
2. Noncompliance with the protocol.

3. A serious or intolerable AE that, in the Investigator's opinion, requires withdrawal from the study, including but not limited to laboratory safety assessments that reveal clinically significant (CS) hematological or biochemical changes from the baseline values, other than changes that are expected for vasopressin antagonists, and symptoms or an intercurrent illness that justifies withdrawal. Mild elevations in serum creatinine or serum sodium are known pharmacodynamic effects of vasopressin antagonists like lixivaptan and are transient and reversible. Therefore, patients should not be withdrawn due to mildly elevated serum creatinine or serum sodium. Cases where eGFR has declined by 25% or more from baseline should be discussed with the Medical Monitor.
4. Lost to follow-up.
5. Other (e.g., pregnancy, development of contraindications of use of study drug).
6. The subject withdraws consent, or the Investigator or Sponsor decide to discontinue the subject's participation in the study.
7. The Investigator will also withdraw a subject if the Sponsor terminates the study.

Upon occurrence of a serious or intolerable AE, the Investigator will confer with the Sponsor. If a subject is discontinued because of an AE, the event will be followed until it is resolved or stable as determined by the Investigator. Any subject may withdraw his or her consent at any time.

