4.2.2 Handling of Withdrawals

Subjects are free to withdraw from the study or study treatment at any time. Subject participation in the study may be stopped at any time at the discretion of the Investigator or at the request of the Sponsor.

Subjects who discontinue study treatment or active participation in the study will no longer receive study drug. When a subject withdraws from the study, the reason(s) for withdrawal shall be recorded by the Investigator on the relevant page of the electronic case report form (eCRF). Whenever possible, all subjects who discontinue study treatment or withdraw from the study prematurely will undergo all end-of-study assessments at the time of ET. Subjects who fail to return for final assessments will be contacted by the site in an attempt to have them comply with the protocol. Methods for follow up will consist of 2 documented phone calls followed by 1 registered letter.

It is vital to obtain follow-up data on any subject withdrawn because of an AE or SAE. In every case, efforts must be made to undertake protocol-specified, safety, follow-up procedures.

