1.0 Version Date: 25 April 2019

Version Number:

20.4...2

Template No: CS\_TP\_BS016 – Revision 5 Reference: CS\_WI\_BS005

Effective Date: 01Apr2018

Palladio Biosciences STATISTICAL ANALYSIS PLAN: PROTOCOL PA-102 Page 19 of 36

repeatedly missing visits)

Not adhering to US Food and Drug Administration regulations or International
 Conference on Harmonisation Guideline for Good Clinical Practice

Major deviations may lead to the subject being withdrawn from the study. All other deviations will be considered minor.

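### Protocol 10.2.2 requires study withdrawal after a major deviation where 4.2.1 only permits it, and a dosed subject withdrawn this way has no planned Day 35 safety visit

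*Protocol*

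**What the plan says.** Protocol 10.2.2 defines a major deviation by the significant extra risk it creates for the subject. Its examples include breaches of the inclusion or exclusion criteria. It says such deviations are serious enough "and will lead to the subject being withdrawn from the study", with a cross-reference to Section 1. Section 1 is the Introduction and holds no withdrawal rule.

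Protocol 4.2.1 is permissive: "A subject may be withdrawn from the study for any of the following reasons". Reason 1 on that list is "Does not meet the protocol inclusion or exclusion criteria"; reason 2 is noncompliance with the protocol.

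Three further provisions fix what withdrawal means for someone already dosed:

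- Section 4.2 ends the subject's study duration at "the date of Early Termination (ET) for subjects who are withdrawn prior to the End of Study assessment".
- The ET assessment is described twice. Section 4.2.1 asks for procedures "which will be the same as those scheduled to be performed prior to discharge from the CRU on Day 8". Section 4.2.2 says that, whenever possible, subjects who stop treatment or leave the study early "will undergo all end-of-study assessments at the time of ET".
- Section 6.1.9.2 records AEs from the start of treatment until the subject exits the study.

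The Non-PK/PD SAP, Section 9.1.1, is also permissive: "Major deviations may lead to the subject being withdrawn from the study".

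**The concern.** Sites hold two instructions for the same person. If a subject is found after dosing to have breached an eligibility criterion in a way that raises risk, 10.2.2 requires withdrawal from the study and 4.2.1 leaves it open. The cross-reference does not help to settle it.

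The stricter reading has the worse result. Stopping the drug may well be right for such a subject. Leaving the study is a different matter, because it ends scheduled observation of someone whom 10.2.2 itself regards as at added risk. Safety and tolerability is a primary objective.

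The liver criteria show what is at stake. Exclusions 14, 15 and 26 screen for liver risk, and Protocol 1.3 describes serious liver injury as the known risk of the related drug tolvaptan. After Day 8 the only scheduled chemistry panel, which includes the liver tests, is on Day 35. A subject dosed in breach of one of these exclusions and then withdrawn has no planned test at that point.

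**Working it through.** No figure in the plan rests on this rule, so the main check is to follow one dosed subject through the text.

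1. **Trigger.** An eligibility breach that raises risk falls under both 10.2.2 (withdrawal required) and 4.2.1 reason 1 (withdrawal possible).
2. **End of participation.** Under 4.2 it is the ET date instead of Day 35.
3. **Assessments.** One ET set is done. Its content is the Day 8 set by 4.2.1 and the end-of-study set by 4.2.2.
4. **New AEs.** Under 6.1.9.2 recording stops at exit, so an AE that begins after ET has no routine route into the database.
5. **AEs already reported.** Under 6.1.9.6 these are followed until resolved, stable, or judged chronic or not clinically significant.

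Next, the laboratory sets still scheduled after ET. The ET day is an assumption. The schedule days come from Tables 12-1 and 12-2, which differ on Day 8.

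| ET on | Sets left, Table 12-1 | Sets left, Table 12-2 | Days to Day 35 |
|---|---|---|---|
| Day 3 | Days 7, 8, 35 (3) | Days 7, 35 (2) | 35 − 3 = 32 |
| Day 6 | Days 7, 8, 35 (3) | Days 7, 35 (2) | 35 − 6 = 29 |
| Day 8 | Day 35 (1) | Day 35 (1) | 35 − 8 = 27 |

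One ET set stands in for the sets listed. At every ET day the Day 35 visit drops out, with its laboratory tests, vital signs and physical examination. The last column is the gap to that visit. It does not measure lost AE questioning, because AEs are elicited at visits. Between Day 8 discharge and Day 35 only three PK draws are scheduled (Day 8 PM, Day 9 and Day 11), possibly by a home nurse.

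For scale, take the formula behind Protocol Table 7-1: P(AE not seen in n subjects) = (1 − p)^n. With n = 8 and p = 0.20 this gives 0.8^8 = 0.168, which reproduces the table. Suppose, as an assumption, that 1 or 2 of 8 subjects in a cohort are withdrawn and not replaced. For an AE that first appears after ET:

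- n = 7: 0.8^7 = 0.210
- n = 6: 0.8^6 = 0.262

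The documents give no basis for choosing between 0, 1, 2 or more such subjects.

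**The case against.** The strongest reply is that 10.2.2 is not the cause. The follow-up is cut by the general withdrawal rules in 4.2, 4.2.2 and 6.1.9.2, which apply equally to a subject withdrawn at discretion under 4.2.1. Making 10.2.2 permissive would restore no visit. This stands, and it shapes the fix. What 10.2.2 adds is to make that outcome compulsory for a group it calls high-risk.

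A second reply is that the two sections can coexist, with 4.2.1 as a general permissive list and 10.2.2 as a stricter rule for the risky subset. That is arguable, but nothing in 4.2.1 signals an exception and the cross-reference leads nowhere, so a site cannot tell which governs.

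Several stronger readings are tempting, and the documents do not support them:

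- **All safety follow-up is lost.** It is not. Section 4.2.2 moves end-of-study assessments to ET where possible, and 6.1.9.6 follows known AEs. Section 4.2.2 also calls for efforts at safety follow-up, in a paragraph on withdrawals for AEs or SAEs, so its reach to deviation cases is unclear.
- **The post-dose diary week is lost.** This is only an inference. Section 5.7.1 ties the diary to the week after the last dose, and no text stops it at withdrawal.
- **The missed Day 7 questionnaire damages tolerability data.** It is missed if withdrawal falls on Days 3 to 6, but it asks about tolerance of the planned doses and says little once drug has stopped.
- **The SAP contradicts the protocol.** SAP 9.1.1 covers a wider class, adding deviations that impair use of the data, and it governs analysis rather than site conduct. It is supporting evidence only.
- **The safety estimand is breached.** SAP 7.2 addresses stopping treatment early and is silent on leaving the study.
- **The retention instruction conflicts directly with 10.2.2.** The sentence "Every effort should be made to keep subjects in the study" sits in the paragraph on subjects who choose to leave.

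**Conclusion.** The concern holds in a limited form. The protocol gives inconsistent instructions for an ineligible, dosed subject at added risk. The stricter one ends participation at ET without providing for a separate Day 35 safety visit or for routine recording of AEs that begin after ET. What clearly goes is late timing: one scheduled visit about four weeks off drug (Day 35 is 35 − 7 = 28 days after the last planned dose), together with the AE window up to it.

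This assumes that sites follow 10.2.2 as written and that the deviation is found after the first dose and before Day 35. A deviation found before dosing or after Day 35 costs no safety follow-up. The number of subjects is unknown. All of them stay in the Safety Analysis Set (Protocol 7.5), and missing data are analyzed as missing, so no planned summary fails. The change is still worth making: the subjects concerned are those the protocol describes as most exposed, and cohorts have only 8 subjects.

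**What to change.** Separate stopping the drug from leaving the study, in three places.

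- **10.2.2.** Replace "and will lead to the subject being withdrawn from the study" and its reference to Section 1 with: *may lead to discontinuation of study drug (Section 4.2.1). A dosed subject whose study drug is stopped remains in the study for AE collection and the scheduled safety assessments through Day 35, unless consent is withdrawn or the subject is lost to follow-up.*
- **4.2.2.** State that every dosed subject who stops drug but has not left the study keeps the Day 35 safety visit, instead of having end-of-study assessments only at ET. Without this edit the first one achieves little, because 4.2.2 now treats stopping drug and leaving the study alike. Writing it for all such subjects avoids following deviation cases more fully than those who stop for an AE.
- **4.2.1.** Add that, for a dosed subject, reasons 1 and 2 lead to stopping study drug and not to ending safety follow-up.

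Sections 4.2 and 6.1.9.2 need no change, since a subject still in follow-up has neither been withdrawn nor exited. The permissive wording of SAP 9.1.1 can stay. The cost is a short amendment with IRB approval, and a few off-drug subjects kept in visits already in Table 12-1.
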